**LIST OF ABBREVIATIONS AND ACRONYMS**

AE	Adverse Event
ALP	Alkaline Phosphatase
ALT	Alanine Aminotransferase
AST	Aspartate Aminotransferase
BUN	Blood Urea Nitrogen
CBC	Complete Blood Count
CFR	Code of Federal Regulations
cGMP	Current Good Manufacturing Practices
CHD	Congenital Heart Defect/Disease
CRP	C-Reactive Protein
CTCAE	Common Terminology Criteria for Adverse Events
DMSO	Dimethyl sulfoxide
DSMB	Data and Safety Monitoring Board
ECG	Electrocardiogram
ECHO	Echocardiogram
eCRF	Electronic Case Report Form
EF	Ejection Fraction
FAC	Fractional Area Change
FDA	Food and Drug Administration
GCP	Good Clinical Practices
Hct	Hematocrit
HgB	Hemoglobin
HIPAA	Health Insurance Portability and Accountability Act
HLHS	Hypoplastic Left Heart Syndrome
IB	Investigator's Brochure
ICF	Informed Consent Form
IND	Investigational New Drug Application
IRB	Institutional Review Board
IV	Intravenous
MNC	Mononuclear Cells
MRI	Magnetic Resonance Imaging
NT-proBNP	N-terminal of the Brain Natriuretic Peptide
PHI	Protected Health Information
PI	Principal Investigator
PRA	Panel-Reactive Antibody
RBC	Red Blood Cell
RV/LV	Right/Left Ventricle
RVEF	Right Ventricular Ejection Fraction
SAE	Serious Adverse Event/Serious Adverse Experience
SUSAR	Serious and Unexpected Suspected Adverse Reaction
TAPSE	Tricuspid Annular Plane Systolic Excursion
TNC	Total Nucleated Cells
TSH	Thyroid Stimulating Hormone
TTE	Transthoracic Echocardiography
UCB	Umbilical Cord Blood

WBC

White Blood Cell

**CLINICAL STUDY SUMMARY**

Title	Phase IIb Study of Intramyocardial Injection of Autologous Umbilical Cord Blood Derived Mononuclear Cells during Stage II Surgical Repair of Hypoplastic Left Heart Syndrome (AutoCell-II)
Running Title	Phase IIb Efficacy Study of UCB-MNC Intramyocardial Injection for HLHS and HLHS Variants
Protocol Number	CSP-4401
Phase	Phase IIb
Study Design	Prospective, Open label, Non-randomized, Observational Study
Overall Study Duration	6 years
Subject Participation Duration	Up to 4 years or until pre-operative work-up for Stage III surgical palliation has been completed or until cardiac transplant, whichever is first
Single or Multi-Site	Multi-Site
Objectives	This study will evaluate the efficacy and safety of UCB-MNC intramyocardial injections performed during Stage II surgical palliation by focusing on short and long-term cardiac function leading up to the pre-operative work-up for Stage III surgical palliation.
Study Purpose	Determine if the delivery of the autologous UCB-MNC product into the myocardium of the right ventricle of the heart at the time of Stage II surgical repair will provide a short-term improvement in cardiac function, while also providing a reduction in the cumulative days of hospitalization following Stage II surgical repair. Additionally, long-term improvement in cardiac function, growth, reaching Stage III surgical repair pre-op work-up and prolonging time to cardiac transplantation or death will be determined. Reaching developmental milestones and quality of life will also be monitored.
Number of Subjects	30-50 treated subjects receiving cell product, along with 30-50 subjects with standard surgical treatment (not receiving cell product).
Study Population	Subjects less than 13 months of age with HLHS or HLHS variant who are undergoing Stage II surgical palliation.
Study Product, Dose, Route, Regimen	The investigational product is autologous MNC derived from UCB at a concentration of 10-30 million TNC per mL. The investigational product will be delivered into the right myocardium via sub-epicardial injections of 0.1 mL per kg body weight to achieve the target dose of 1-3 million TNC per kg body weight.
Time and Duration of Administration	A single treatment will be administered intraoperatively upon the successful completion of the planned Stage II surgical repair.

Reference therapy	Control cohort of 30-50 subjects, enrolled in the control arm of this study, not receiving the cell product, which will be enrolled and followed using the inclusion/exclusion criteria and follow-up requirements outlined herein.
Treatment Assignment	When possible, prior to enrollment in this study, expecting parent(s) with the prenatal diagnosis of HLHS or HLHS variants will be offered enrollment in a separate protocol for the collection of UCB. The collected UCB will be used for UCB-MNC treatment described herein if the subject is enrolled in and meets all eligibility criteria for this open-label study, and if the UCB-MNC manufactured product is determined to be acceptable for release to the investigational site for clinical use. Subjects without frozen UCB-MNC product available or with frozen UCB-MNC that is NOT acceptable for clinical use, or that choose not to participate in the treatment arm may be enrolled in the control arm of this study.
Primary and Secondary Short-Term Endpoints	
The primary short-term efficacy endpoint regarding the cell product and its delivery procedure is:
 
Change in right ventricular cardiac function at 3 months post-Stage II surgery compared to baseline, measured by apical fractional area change (FAC), circumferential strain, and longitudinal strain all as determined by echocardiography.
 
Secondary short-term safety and efficacy outcomes in order of their relevance and importance in this clinical study are:
 
 
1) Change in right ventricular cardiac function between baseline and hospital discharge for Stage II surgery, measured by echocardiogram.
 
2) Cumulative days of hospitalization per patient at 1 and 3-months post Stage II surgery.
 
3) Change in weight, heart rate, and oxygen saturation at 3-months post Stage II surgery compared to baseline.
 

Primary and Secondary Long-Term Endpoints	
The primary long-term efficacy endpoint regarding the cell product and its delivery procedure is:
 
Change in right ventricular cardiac function at 12 months post-Stage II surgery compared to baseline, measured by echocardiogram.
 
Secondary long-term safety and efficacy endpoints in their order of relevance and importance in this clinical study are:
 
 
1) Change in weight every 6 months post-Stage II surgery compared to baseline.
 
2) Change in heart failure medication taken every 6 months post-Stage II surgery compared to baseline.
 
3) Change in arrhythmia medication taken every 6 months post-Stage II surgery compared to baseline.
 
4) Success of subject being scheduled for Stage III surgical repair.
 
5) Time (days) until listed for cardiac transplantation, or death following the 6-month follow-up.
 
6) Change in right ventricular function at Stage III surgery pre-op work-up compared to baseline, obtained by echocardiogram and cardiac catheterization.
 

Statistical Methodology	
Quantitative outcomes, like FAC, at specified time post-surgery, will be analyzed using analysis of covariance to estimate the difference in means between the cell-based therapy and control groups after adjusting for the baseline value (the measured value of the same variable, e.g. FAC, at the time of Stage II surgery). Categorical outcomes, like able to undergo Stage III palliation surgery, will be compared between groups using a chi-square test. Time-to event outcomes, like time until listing for cardiac transplant, will be compared using the Kaplan-Meier method and log-rank test. We will similarly do analyses of other variables based upon this patient subset. In secondary analyses we will also fit models which allow the treatment effect (mean difference between the cell-therapy group control groups) to depend on baseline cardiac function measures or other baseline values. This will be done by using the linear, logistic and Cox regression models as appropriate.

Imaging Core Lab	
M. [name] (Core Lab Director) Mayo Clinic Pediatric and Adolescent Medicine [name] [name]

Contract Manufacturing Organization	
ReGen Theranostics, Inc. [name] [name]

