## 3 STUDY DESIGN

### 3.1 General Design

This Phase IIb study is a multicenter, prospective, open-label, non-randomized, observational study designed to evaluate the efficacy and safety of UCB-MNC delivered into the right ventricular myocardium of subjects with HLHS or HLHS variants with right ventricular dependent single ventricular CHD at the time of a planned Stage II surgical repair. This will be achieved by comparing the data collected in the treatment group (Arm A) to the equivalent data collected in the control group (Arm B), adjusting for baseline.

The concurrent control arm (Arm B) must meet identical study eligibility criteria as the treatment arm (Arm A), except for the requirements related to UCB-MNC product acceptability and DMSO sensitivity. The control arm will undergo the same planned Stage II surgical repair without the investigational cell delivery add-on procedure and will follow-up post-surgery in the same manner as the treatment arm (see Section 6 of this protocol).

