### 3.3 Long Term Endpoints

The primary long-term efficacy endpoint regarding the cell product and its delivery procedure is:

Change in right ventricular cardiac function at 12 months post-Stage II surgery compared to baseline, measured by echocardiogram.

Secondary long-term efficacy safety endpoints in their order of relevance and importance in this clinical study are:

- 1) Change in weight every 6 months post-Stage II surgery compared to baseline.
- 2) Change in heart failure medication taken every 6 months post-Stage II surgery compared to baseline.
- 3) Change in arrhythmia medication taken every 6 months post-Stage II surgery compared to baseline.

- 4) Success of subject being scheduled for Stage III surgical repair.
- 5) Time (days) until listed for cardiac transplantation, or death following the 6-month follow-up.
- 6) Change in right ventricular function at Stage III surgery pre-op work-up compared to baseline, obtained by echocardiogram, cardiac MRI, and cardiac catheterization.

Additional variables may be assessed in an exploratory manner.

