### 7.1 Sample Size Determination

Sample size calculations were performed using alpha = 0.05 and assume equal variance across study arms. With 50 subjects per arm we will have 80% power to detect an effect size as small as 0.57 in difference in cardiac function measures. This is built on the assumption all subjects from both arms have complete data at baseline and 3-month follow-up visits. In the event of attrition or incomplete data in 40% of participants, equal across study arms, the study has 80% power to detect an effect size as small as 0.74 in difference in cardiac function measures.

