#### Secondary Outcomes

Quantitative long-term outcomes will be analyzed like the primary long-term efficacy outcome of apical fractional area change. Yes/no outcome variables like “able to undergo Stage III palliative surgery” will first be analyzed by describing percent by group and the groups

compared using a chi-square test. We will analyze time-to-event outcomes, like time to listing for cardiac transplant or death, first describing naïve rates with the Kaplan-Meier method and then using Cox regression models including terms for treatment group and baseline cardiac function. If the primary analysis suggests dependency of treatment on cardiac function, we will also repeat these analyses considering cardiac function as an effect modifier by including interaction terms between group and baseline cardiac function.

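### The two medication-change endpoints are assigned to no analysis, and the first-line categorical test they could fall under has no baseline term in a non-randomised comparison

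*Combined protocol and SAP*

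**What the plan says.** The Clinical Study Summary and Section 3.3 list, as second and third long-term secondaries, "Change in heart failure medication taken every 6 months post-Stage II surgery compared to baseline" and "Change in arrhythmia medication taken every 6 months post-Stage II surgery compared to baseline". No drug list, unit, scoring, direction or tested visit follows, there or in Section 7.

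Two first-line routes exist. For numerical outcomes, Section 7.4.4 says "Quantitative long-term outcomes will be analyzed like the primary long-term efficacy outcome of apical fractional area change", that is, ANCOVA with the baseline value. For the rest, the Summary says "Categorical outcomes, like able to undergo Stage III palliation surgery, will be compared between groups using a chi-square test". Section 7.4.4 repeats the chi-square for yes/no outcomes. Neither place says which route medication takes.

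The Summary also plans secondary linear, logistic and Cox models in which the treatment effect may depend on baseline cardiac function or other baseline values. Section 7.4.4 limits its version to baseline cardiac function, and applies it only if the primary analysis suggests dependency. Section 7.4.5 sends arrhythmia medication to the safety analysis as well, without coding.

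The study is non-randomised. Section 3.1 says that Arm A will be compared "to the equivalent data collected in the control group (Arm B), adjusting for baseline".

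**The concern.** Arm membership depends on whether a usable cord blood product exists and on parental choice, so the arms may differ in medication before surgery. A test without baseline medication can then read that difference as an effect of the cells. A coding without direction can hide a real effect, because a child weaned off a drug and a child newly started on one both count as changed.

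Section 7.3 assesses significance in the listed order. These two endpoints stand ahead of Stage III scheduling and of transplant listing or death, so an error here reaches the clinical endpoints behind it. The study is also open-label with five interim analyses. A coding that is not fixed now could be chosen after results are known, and the codings give different answers.

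**Working it through.** **The plan's own figure.** Section 7.1 gives alpha 0.05 and states: "With 50 subjects per arm we will have 80% power to detect an effect size as small as 0.57". The normal approximation is (1.960 + 0.842) × √(2/n). This gives 0.560 at n = 50 and 0.723 at n = 30 (after 40% attrition). The two-sided t-test gives 0.566 and 0.736, so the stated 0.57 and 0.74 reproduce. They concern cardiac function. No power is stated for medication.

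**Assumed inputs.** The documents give no medication rates, so every rate below is an assumption. Let b be baseline use, s the share of users who stop, and i the share of non-users who start.
- Use at follow-up = b(1 − s) + (1 − b)i
- Decreased = b·s
- Increased = (1 − b)·i

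**No cell effect.** Take s = 20% and i = 10% in both arms, with b = 50% treated and 70% control.
- Use at follow-up: 0.50 × 0.80 + 0.50 × 0.10 = 45%, against 0.70 × 0.80 + 0.30 × 0.10 = 59%.
- At 50 per arm, pooled p = 0.52 and SE = √(0.52 × 0.48 × 2/50) = 0.100. So z = 0.14/0.100 = 1.40, and the chance of rejecting is about Φ(1.40 − 1.96) = 29%. Simulation gives 31%.
- Decreased: 10% v 14%. Increased: 5% v 3%. The distortion is smaller here, but not zero.

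Simulated rejection rates with no cell effect (20,000 runs per row, nominal 5%, 50 per arm):

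| Baseline use | Stop / start | On/off chi-square | Decreased/same/increased chi-square | Mantel-Haenszel by baseline use |
|---|---|---|---|---|
| 50% v 50% | 20% / 10% | 5–6% | 4% | 5% |
| 55% v 70% | 20% / 10% | 20% | 6% | 5% |
| 50% v 70% | 20% / 10% | 31% | 7–8% | 5% |
| 50% v 70% | 50% / 20% | 10% | 18% | 5% |
| 40% v 70% | 50% / 10% | 25% | 33% | 5% |

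At 30 per arm, the third row becomes 20% on/off, about 5% for three categories and 5% stratified. The last row becomes 16%, 20% and 5%. With equal baselines there is no excess, so the excess comes from the baseline imbalance. The three-category coding is distorted because a child on no drug cannot decrease, so the share able to move down depends on baseline use.

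**Direction.** Assume a real benefit: users stop 50% v 20%, non-users start 10% v 40%, and baseline use is 50% in both arms.
- Any change, treated: 0.50 × 0.50 + 0.50 × 0.10 = 30%.
- Any change, control: 0.50 × 0.20 + 0.50 × 0.40 = 30%.
- At 50 per arm, power is about 5% for any change, 72% for the three-category chi-square and 92% for the baseline-stratified test. At 30 per arm, the stratified test has 74%.

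**The case against.** **The chi-square is not the plan's only test.** A reader might infer that it is, but the Summary also plans logistic models with other baseline values. This limits the point without removing it. Those models are secondary, are framed as effect modification, and do not name baseline medication.

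**The plan never calls these endpoints categorical.** A drug count analysed by ANCOVA with its own baseline already fits the text and avoids both faults. That is correct. The plan does not choose that route, and the chi-square route is equally open.

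**Each fault belongs to a particular coding.** On/off use carries the baseline difference, and any-change cancels weaning against escalation. A decreased/same/increased chi-square does not cancel, and at the milder rates it rejects only 7–8%. This stands, but the same coding reaches 18–33% with more stopping or a larger imbalance. The complete cancellation is also a chosen case: if control non-users start at 20% or 10% instead of 40%, power of the any-change test rises to about 21% or 44%.

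**Total dose.** A reader might also expect total dose to rise with body weight and look like escalation. The documents do not support building on this: nothing says that total dose is the variable, and Section 4.7 does not name dose as a recorded field.

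**Conclusion.** The concern holds in this form: two ordered secondary endpoints have no assigned analysis, and the first-line categorical test open to them omits baseline medication where Section 3.1 promises baseline adjustment. It does not follow that every analysis available under the plan is wrong.

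Under the assumed rates, with no cell effect and 50 per arm, the false-positive rate is about 31% for on/off use at 50% v 70% baseline use with 20% stopping and 10% starting. It is about 7–33% for decreased/same/increased over the unequal-baseline settings from 50% v 70% upward in the table, against about 5% with stratification. These figures show sensitivity. They do not forecast this trial, and a larger imbalance would give higher rates. If the arms turn out alike in baseline medication, the bias disappears and only the coding problem remains. This should be corrected; it does not touch the primary endpoints.

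**What to change.** In Section 3.3 items 2 and 3 and Section 7.4.4, take both endpoints out of the chi-square route and state:
- the list of heart-failure drugs and of arrhythmia drugs, fixed before any comparison by arm;
- which 6-monthly visit is tested (four years of follow-up gives up to 4 × 2 = 8 time points), with the other visits descriptive;
- the outcome: number of drugs in the class at that visit, or fewer/same/more than at baseline;
- the comparison: a proportional-odds or logistic model with arm and baseline number of drugs as terms, or a Mantel-Haenszel test stratified by baseline use.

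Apply the same adjusted analysis to arrhythmia medication in Section 7.4.5. Do not score dose changes unless the sponsor confirms that dose is captured.

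Baseline medication and later changes are already collected at the scheduled contacts, so no visit or procedure is added. Section 4.7 leaves changes during hospital stays out of the eCRFs, so the sponsor should confirm that the drugs in use at the tested visit can be read from the log. The cost is SAP wording and some coding of the log. Adjustment for baseline medication does not remove other confounding between non-randomised arms, and the report should say so.

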## 1 INTRODUCTION

This document is a protocol for a human research study involving subjects who require surgical palliation for HLHS and HLHS variants. This study aims to deliver an autologous cell-based product at the time of planned Stage II surgery and will be carried out in accordance with the applicable FDA regulations and this protocol. Based on the safety data from the initial 10 treated subjects in our Phase I safety study, we herein propose this Phase IIb efficacy study using autologous UCB as the source for MNC that will be delivered into the myocardium of the right ventricle. The objective of this study is to evaluate the short and long-term surrogate markers of safety and efficacy of autologous UCB-MNC intramyocardial injections. This add-on procedure is anticipated to pose little risk to the subject and has the potential to foster a new strategy that leverages the regenerative capacity of the pediatric heart during clinically mandated, multi-stage surgical repair.

This study will not be randomized as our preliminary data (summarized in 1.4) suggests that cell-based therapy may be beneficial to this high-risk patient population with little evidence to indicate there are any measurable safety concerns. This safety and efficacy data are consistent with our ongoing pre-clinical studies that are conducted using a double-blinded, randomized study design. Previously collected autologous umbilical cord blood in the UCB Collection Study will be used in the treatment arm of this open-label study. Controls will be screened using identical clinical inclusion/exclusion criteria that either do not have UCB collected as part of the UCB Collection Study, UCB-MNC product that is determined to be unacceptable for investigational use, or that choose to not participate in the treatment arm of this study.

This protocol is designed to evaluate the clinical outcomes following intramyocardial delivery of autologous UCB-MNC and is being conducted to investigate this product and its delivery procedure as a potential new therapy to strengthen the right ventricle of patients with HLHS or HLHS variants. The central hypothesis of this study is that the delivery of the autologous UCB-MNC product into the myocardium of the right ventricle of the heart at the time of Stage II surgical repair will provide a short-term improvement in cardiac function, reaching growth and developmental milestones, and quality of life, while also providing a reduction in the cumulative days of hospitalization following discharge for the Stage II surgical repair. It is also hypothesized that the autologous UCB-MNC product and its delivery procedure will ultimately provide long-term improvement in cardiac function, reaching growth and developmental milestones, reaching Stage III surgical repair pre-operative work-up, prolonging time to cardiac transplantation or death, and improving quality of life.

The safety and efficacy endpoints will be evaluated by the DSMB at least annually. This will determine the appropriateness of continued enrollment in both arms of this Phase IIb study. By demonstrating reasonable efficacy and safety of this product and its delivery procedure in this study, future definitive studies may be designed with the goal to establish a marketable regenerative therapy to treat this rare, life-threatening congenital heart disease as quickly as possible.

## 1.1 Background

HLHS, and HLHS variants that require single ventricle palliation, are severe forms of CHD with morphological right ventricles that consist of multiple obstructions to flow through the left heart and aorta, as well as hypoplasia (underdevelopment) of the left ventricle. This combination of defects requires the affected individual to undergo surgical palliation to create a functional “single ventricle” circulation [1]. Patients are diagnosed with HLHS or HLHS variants when hypoplasia of the mitral valve, left ventricle and/or aortic valve does not allow the left ventricle to support systemic/aortic circulation. Hypoplasia is defined based upon the aortic annular dimensions, and/or left ventricular cavity dimensions and volume. Patients with HLHS have valves and chamber dimensions more than two standard deviations below the expected newborn mean value (Z scores < 2.0). Ascending aorta and aortic arch hypoplasia with coarctation often coexist with HLHS but are not defining features of the diagnosis.

For years, families were faced with making a choice between comfort care, multistage conventional surgical palliation or cardiac transplantation within the first days of life. As clinical management has improved to decrease mortality to 10-20% [2], the majority of families in the United States are electing for surgical management rather than comfort care only, with the expectation that individual patients will have ~70% chance of achieving the final Fontan circulation by the age of 5 [3]. This therapeutic option requires several palliative surgeries designed to reconstruct the patient’s circulatory system into one that can be sustained by a single right ventricle. The “single ventricle” approach requires the right ventricle to perform as the primary circulatory pump for the entire body. After initial surgery, the right ventricle is presented with the obligatory volume overloads and chronic cyanosis. These insults, combined with the need for multiple open-heart surgeries and the effects of chronically increased right ventricular myocardial afterload, often lead to progressive ventricular dysfunction and potentially life-threatening complications (i.e. protein losing enteropathy and congestive heart failure).

Central to the hypothesis of this study is the evidence that cardiac dysfunction is a life-long complication for these individuals. Specifically, the risk of morbidity and mortality does not significantly improve even for those individuals that are able to successfully achieve Stage III Fontan circulation. Evidence indicates that 40% of patients post-Stage III either require heart transplantation, major surgical revisions, or do not survive after 12 years [4]. Furthermore, right ventricular ejection fraction (RVEF) less than 40% as measured by echocardiogram after one year post-Stage II surgery was the strongest predictor of the nearly 5% of patients that died or require cardiac transplantation within this early time period [5]. Additionally, the most common shunt used today has improved 1-yr survival rates in the Single Ventricle Trial (RV to PA conduit) yet is now associated with a long-term decline in right ventricular function and a trend towards decreased transplant-free survival likely due to ventriculotomy required in the RV at Stage I [5]. Most concerning is the reality that hypoplastic left heart syndrome patients may have the highest risk of developing right heart failure throughout the course of their clinical care for this condition [6].

Moreover, the routine imaging by echocardiography is not able to detect early ventricular dysfunction in the single right ventricle, which may be detected with the use of magnetic

resonance imaging (MRI) in these patients [7, 8]. The right ventriculotomy also leads to an aneurysmal, dyskinetic segment in the right ventricular outflow tract, seen only by MRI which adversely affects overall right ventricular systolic function in these patients [9]. Finally, cardiac transplantation is not a perfect choice to manage these patients for multiple reasons that include 4x increased morbidity and mortality rate in the high-risk single ventricle patients and only a 63% survival after 3 years for transplanted single ventricle patients [10]. Long-term mechanical support is not a practical option for these patients.

Although outcomes have improved compared to the previous decades, these patients that are dependent on single morphological right ventricles are clearly still at significant risk of long-term morbidity and mortality. As a result, the development of regenerative therapies is becoming increasingly important to minimize the risk of long-term ventricular failure in patients with single ventricle circulatory systems. Thus, our goal is to strengthen and re-engineer the native right ventricle of CHD children using a stem cell-based regenerative therapy.

Children with single ventricle circulatory systems need regenerative applications to strengthen their right ventricle and sustain long-term pressure overload in order to minimize the need for cardiac transplantation. The current results from the first 10 subjects treated with the UCB-MNC product in our Phase I study provide the primary motivation to proceed with this Phase IIb study. The clinical necessity of open cardiac surgery allows the investigational UCB-MNC intramyocardial treatment described herein to be an “add-on” procedure with minimal risks to the subject.

Furthermore, studies conducted in Japan have been published that include a wide-spectrum of CHD patients using autologous cells derived from heart biopsy samples have demonstrated improvement in cardiac function as measured by cardiac MRI and echocardiogram with three years of follow-up. Despite the limitations of lack of randomization, heterogeneous patient population, wide range of ages, and different surgical approaches; these studies provide the best available data and suggest a measurable and meaningful improvement in treated patients [11].

